### **9.7.1. Analysis of Demographics and Baseline Characteristics**

Demographic and baseline characteristics will be summarized with descriptive statistics for the galcanezumab exposed, CGRP antagonist-unexposed migraine and general population, non-migraine groups. Characteristics can be compared with the exposed group to assess potential differences. These data will be reviewed for potential confounding factors that could affect the interpretation of comparisons of study outcome data with that of comparator data. Further details will be included in the Statistical Analysis Plan (SAP).

### **9.7.2. Statistical Methods**

Overall and stratum-specific (e.g., timing of exposure to galcanezumab (prior to conception vs. during pregnancy, as well as trimester of exposure), maternal age group) point estimates and 2-sided 95% confidence intervals will be calculated using the exact binomial distribution for prevalence of congenital malformations among evaluable patients, preterm birth and SGA among evaluable patients with live births, preeclampsia and hypertension in pregnancy and infant growth and development through one year for each of the galcanezumab exposed, CGRP antagonist-unexposed migraine and general population, non-migraine groups.

If applicable, frequencies of the events of interest will be presented by pregnancy outcome.

Most structural defects have their origins in the first trimester of pregnancy, the period of organogenesis. In addition to overall prevalence of observed MCM, the analysis of MCMs will be stratified by trimester of earliest exposure to galcanezumab. The prevalence of combined MCMs reported to the study will be calculated as a proportion with the number of observed MCMs as the numerator and the number of live births as the denominator, among women with first trimester exposure. CDC MACDP uses these figures to calculate the prevalence, and in order to compare the observed study prevalence with the background prevalence, it is decided to use the same method. Pregnancy losses occurring at or after 20 weeks' gestation with reported MCMs will be included in the numerator of the estimate of prevalence for MCMs as a conservative approach. This method also allows comparison of outcomes with the CDC MACDP. The reason MACDP uses this method is because a slight overestimate is preferred to a potential underestimate. This is due to not taking into account stillbirths in the denominator (but counting the MCM's recognized in stillbirths in the numerator). However, given the very low prevalence of stillbirths as pregnancy outcomes in the general population, this is only a very small possible overestimate. The prevalence of observed MCMs in exposed cases will be compared with the most recent reported prevalence of the CDC MACDP. Additionally, if a sufficient sample size is attained for each trimester exposure group, it may be possible to compare the prevalence of MCMs among exposures to galcanezumab in the first trimester versus

those in the second or third trimester combined, in addition to the migraine and general population, non-migraine controls.

Only congenital malformation cases meeting the CDC MACDP criteria for a major defect or with three or more minor malformations (e.g., conditional defects) will be included in the primary analysis. In the absence of a major malformation, one or two minor defects do not constitute a MCM according to the CDC MACDP classification; therefore, they will be listed in the report, but not counted as an MCM case in the primary analysis.

The prevalence of preterm births and SGA will be calculated as proportions, with the number of live births as the denominator. The prevalence of preterm birth and SGA in exposed cases will be compared with that in the two comparison groups, as well as with published data, including the most recent reported data by the CDC NVSS. Because MCMs and also multiple gestation pregnancies are often associated with preterm birth and SGA, these infants will be excluded from analyses of these outcomes and will not be counted in the numerator or denominator when prevalence is determined.

For this study, gestational weeks are estimated from the most reliable EDD as reported by the HCP. If a CEDD is provided by the HCP, it will be used instead. The date of conception will be calculated as the most reliable EDD minus 38 weeks. If the EDD is not available or never estimated, the first day of the LMP may be used to estimate gestational age. The second trimester will be considered to begin at week 14, and the third trimester, at week 28. If there is a discrepancy between gestational age calculated from LMP and reported gestational age, the HCP will be asked to verify the data.

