#### 9.2.2. Study Participants

The study population will include pregnant women within the US who were treated with galcanezumab as part of routine care at any time during pregnancy or up to 4 months prior to conception, as well as pregnant women with migraine not exposed to CGRP antagonists and pregnant women without migraine. Eligible pregnant women may self-enroll or voluntarily be enrolled by their HCP. Enrollment should occur as early in pregnancy as possible, preferably before any prenatal testing has occurred.

Enrollment and data collection will be coordinated through the Registry Coordination Center (RCC). The minimum eligibility criteria required for enrollment are as follows:

Inclusion:

- Pregnant at the time of enrollment

- Sufficient information to confirm eligibility for either the galcanezumab, unexposed to CGRP antagonist, or general population cohort
  - Galcanezumab cohort: at least one injection of galcanezumab occurred during the pre-pregnancy or pregnancy period (as defined in Section 9.3.1) without any other CGRP antagonist exposure during this time and at which date
  - Unexposed to CGRP antagonist cohort: no exposure to a CGRP antagonist during the pre-pregnancy period (as defined in Section 9.3.1)
  - General population (without migraine) cohort: no diagnosis of migraine
- Sufficient information to determine whether the outcome of pregnancy is known at the time of registry reporting to determine whether the pregnancy exposure reported to the registry is prospective (i.e., before the outcome or perceived outcome of pregnancy is known) and eligible for enrollment
- Reporter (e.g., participant, maternal HCP) contact information to allow for follow-up
- Permission to contact the patient's and her infant's HCPs
- Patient informed consent to participate

Exclusion:

- Retrospective (i.e., a pregnancy exposure to the Registry drug reported after the pregnancy has ended or for an ongoing pregnancy in which an abnormal condition was identified on a prenatal test) cases are ineligible for enrollment
- Women under 18 years of age

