### **9.4.3. Operational Exposure Definition**

When a pregnant woman enrolls in the study, she will be asked when she was last treated with galcanezumab. When a pregnant woman is enrolled by her HCP, the HCP will provide this information. The pregnant woman will then be asked to provide a medical release that allows the RCC to confirm galcanezumab treatment with the appropriate source. Reported galcanezumab injection at any time during pregnancy (from four months prior to LMP until pregnancy outcome) will constitute a fetal exposure. Galcanezumab exposure will be further categorized by earliest trimester of exposure.

For this study, gestational weeks will be estimated from the most reliable EDD as reported by the HCP or the pregnant woman. If a CEDD is provided by the HCP, it will be used instead. The date of conception will be calculated as the most reliable EDD minus 38 weeks. If the EDD is not available or never estimated, the first day of the LMP may be used to estimate gestational age. The second trimester will be considered to begin at week 14 after LMP, and the third trimester at week 28. If there is a discrepancy between gestational age calculated from LMP and reported gestational age, the HCP will be asked to verify the data.

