## 9.5. Study Size

The study aims to enroll a minimum of 420 prospectively enrolled evaluable pregnant women with galcanezumab exposure. Approximately 420 galcanezumab exposed pregnancies are needed to have 80% power to detect a 2.0 fold difference in the baseline risk of major malformations (2.78%) relative to women in the general population.

Assuming 10% loss to follow-up, it is anticipated that approximately 470 patients need to be enrolled. Research indicates that approximately 83% to 95% of pregnancies enrolled in pregnancy exposure registries result in a live birth (Covington et al. 2010), resulting in a lower estimate of approximately 350 and an upper estimate of 400 live births.

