#### ***Subgroup Analyses and Stratification***

Analyses will be stratified by trimester of exposure and other subgroups of interest, potentially including gestational age at enrollment and maternal age. Additional details on subgroup analyses and stratification will be described in the SAP.

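### Trimester strata defined by earliest exposure have different entry times, so the optional first-versus-later MCM contrast and the third-trimester preterm proportion can be biased with no drug effect

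*Protocol*

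**What the plan says.** **Stratum definition.** Protocol 9.4.3: "Galcanezumab exposure will be further categorized by earliest trimester of exposure". The second trimester starts at week 14 and the third at week 28. Section 9.7.2 applies the same earliest-exposure rule to the MCM analysis.

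**Entry rule.** Under 9.2.2 a woman must be pregnant at enrolment. For the galcanezumab cohort she must already have had at least one injection. A case is retrospective, and so ineligible, if reported after the pregnancy ended or "for an ongoing pregnancy in which an abnormal condition was identified on a prenatal test". The same section asks for enrolment as early as possible, ideally ahead of prenatal testing.

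**Planned use.** Where the trimester groups are large enough, 9.7.2 leaves room to "compare the prevalence of MCMs among exposures to galcanezumab in the first trimester versus" later first exposure. It describes the reference groups as "those in the second or third trimester combined, in addition to the migraine and general population, non-migraine controls". The section also gives stratum-specific binomial proportions with exact intervals, including preterm birth among live births. Under Subgroup Analyses and Stratification: "Analyses will be stratified by trimester of exposure and other subgroups of interest", with gestational age at enrolment named only as a possibility.

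**Disclosure.** Section 9.9 says that enrolling women after a normal prenatal test may lower the overall MCM risk, and that early spontaneous abortions will be missed. It does not say that either effect differs between exposure strata.

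**The concern.** The injection that defines the stratum is also a condition of entry. A woman whose first injection falls in week 20 cannot be in the exposed cohort at week 10, and if a defect has been found by the time she is reported she is ineligible. A woman exposed in week 4 may enrol in week 8, and a defect found at week 18 then counts. The two strata are left-truncated at different gestational ages.

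For MCMs, the reference group loses more prenatally detected defects through eligibility than the index group does. Section 9.7.2 introduces the trimester analysis by pointing to organogenesis, so a first-trimester excess would naturally be read as a teratogenic signal. For preterm birth, a third-trimester starter has already escaped every delivery before her entry week, so a simple proportion in that stratum is too low and could falsely reassure.

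**Working it through.** **1. The plan's own figure, for scale.** Section 9.5: "The study aims to enroll a minimum of 420 prospectively enrolled evaluable pregnant women with galcanezumab exposure", for 80% power against a 2.0-fold increase over 2.78% (that is, 5.56%). Alpha is not stated; two-sided 0.05 is assumed. For a comparison with a fixed rate:

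n = [1.96·√(0.0278·0.9722) + 0.8416·√(0.0556·0.9444)]² / 0.0278² = (0.3222 + 0.1929)² / 0.000773, about 344 live births.

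Then 344/0.83 = 414 pregnancies, close to 420. Also 420/0.9 = 467 (stated as about 470), and 420 × 0.83 to 0.95 = 349 to 399 live births (stated as 350 to 400). The figure reproduces. It is a benchmark against the general population; the trimester contrast was not sized.

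**2. MCM ratio with no drug effect.** Let d1 and d2 be the shares of countable defects already known before entry in the first-trimester and later strata. The protocol gives neither, so both are assumed. To a close approximation the null ratio is (1 − d1)/(1 − d2):

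| d1 | d2 | ratio |
|---|---|---|
| equal | equal | 1.00 |
| 0.15 | 0.30 | 0.85/0.70 = 1.21 |
| 0.10 | 0.40 | 0.90/0.60 = 1.50 |
| 0.05 | 0.50 | 0.95/0.50 = 1.90 |

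The exact form, prevalence = p(1 − d)/(1 − p·d) with p = 0.0278, agrees: 0.10 against 0.30 gives 2.51% against 1.96%, ratio 1.28. The extreme corner of 0 against 0.50 gives 2.78% against 1.41%, ratio 1.97.

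**3. How much the contrast can show.** Expected MCMs in 350 to 400 live births: 0.0278 × 350 = 9.7 to 0.0278 × 400 = 11.1. With 350 live births, of which 50, 100 or 150 are in the late stratum, power for a true 2-fold difference (5.56% against 2.78%, two-sided 0.05) is 8%, 16% or 23%. The bias would mainly distort a point estimate.

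**4. Preterm proportion by week of entry.** Assumed births: 0.5% at 24–27 weeks, 1.0% at 28–31, 1.2% at 32–33, 7.3% at 34–36, 90% at term. With entry uniform on weeks a to b, a birth at week g is retained with probability (g − a)/(b − a), held between 0 and 1.

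- Entry 14–28: preterm retained 0.5 × 0.857 + 9.5 = 9.93; 9.93/99.93 = 9.9%, ratio 0.99.
- Entry 28–32: 1.0 × 0.5 + 1.2 + 7.3 = 9.0; 9.0/99.0 = 9.1%, ratio 0.91.
- Entry 28–36: 1.0 × 0.25 + 1.2 × 0.625 + 7.3 × 0.917 = 7.69; 7.69/97.69 = 7.9%, ratio 0.79.
- Entry 28–40: 1.0 × 0.167 + 1.2 × 0.417 + 7.3 × 0.625 = 5.23. With term births uniform over 37–41.5 weeks, 90 × 0.917 = 82.5 are retained, so 5.23/87.7 = 6.0%. A simulation of 4 million births gives 5.9%, ratio 0.59.

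A second assumed distribution (72% of preterm births at 34–36 weeks, entry at 28–38) gives 6.5% for a true 10%, 5.2% for 8% and 7.9% for 12%. Under it, first-trimester-exposed women who enrol evenly over weeks 6–36 show 9.35%, against 10.0% if they enrol at weeks 6–14. Enrolment timing therefore matters in every stratum.

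**5. Would a week-28 landmark repair it?** Under the distribution in step 4, controls still pregnant at week 28 have 9.5/99.5 = 9.55% preterm. The ratio moves only from 0.59 to 5.9/9.55 = 0.62, or from 0.79 to 7.9/9.55 = 0.83. Most of the truncation happens after week 28.

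**The case against.** The strongest reply is that the MCM contrast is conditional on sample size, that subgroup and confounding details are left to the SAP, and that gestational age at enrolment is already named as a possible subgroup. This lowers the urgency. It does not remove the point, because the stratum definition, the entry rule and the crude contrast are fixed in the protocol, and the one variable that would control the problem is optional and not tied to the contrast.

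Several stronger readings are tempting, and the documents do not support them:

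- *A reader might infer that the late strata hold only women with normal tests.* Section 9.2.2 excludes known abnormal findings; untested women qualify.
- *A reader might infer that the contrast must show a near 2-fold artefact.* The detection shares are assumed, and 1.9 pairs the lowest assumed share with the highest. First-trimester women who enrol late pass the same entry rule, and with equal timing the ratio is 1.00. The 9.7.2 numerator adds only losses at or after 20 weeks, so defects found early and ending before then may drop out of the first-trimester stratum too and narrow the gap, although the case definition in 9.3.2.2 is wider.
- *A reader might infer that trimester-specific preterm comparisons with controls are planned.* Section 9.7.2 compares exposed cases as a whole with the control groups; by stratum it gives only proportions and intervals. Controls must also be pregnant at enrolment and may enrol late, so not all early births are kept in those cohorts.
- *A reader might infer that both late strata are biased for preterm birth.* The second-trimester ratio is 0.99.

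**Conclusion.** The point holds in this limited form. The eligibility rule and the earliest-exposure strata together produce different entry times. To the extent that enrolment is later in the late stratum, the first-versus-later MCM ratio is pushed upward with no drug effect: from 1.0 up to about 1.9 under the assumed detection shares. The third-trimester preterm proportion is biased low, to roughly 5.9% to 9.1% against an assumed 10%, depending on when first injections occur. The second-trimester effect is negligible.

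The direction follows from the protocol's text. The size rests on assumed detection shares, an assumed gestational-age distribution and uniform entry times. The MCM contrast is optional and would rest on about ten or eleven events, so the risk is a misread point estimate more than a formal false positive. Section 9.9 covers only the overall effect.

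**What to change.** Amend 9.7.2, with matching text in the SAP.

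1. If the first-versus-later MCM contrast is run, make gestational age at enrolment a required adjustment or matching factor, so that women enrolled at similar gestational weeks are compared. Add restriction to enrolment at or after week 14 as a sensitivity analysis. It should not be the main analysis, because it leaves timing differences beyond week 14 and discards the early enrollees whom the registry most wants. State that the crude contrast will not be interpreted as a teratogenic signal.
2. Label the third-trimester preterm proportion as conditional on being undelivered at first injection and enrolment. Make any comparison of it with controls by risk sets: controls enrolled and still pregnant at the gestational week when the exposed woman entered. A single week-28 landmark is not enough.
3. Add to 9.9 that the selection by prenatal testing and by survival of the pregnancy to entry can differ between exposure strata.

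The registry already records injection dates, LMP and due dates, and prenatal test dates and results, and its data collection starts at enrolment, so no new data are needed. The cost is wording, some programming, and less precision in a contrast that is already sparse.

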#### **9.7.2.1. Methods to Control for Confounding and Effect Modification**

For analyses of associations between pregnancy outcomes and events of interest, confounding and effect modification will be evaluated. A detailed description of these analyses will be available in the SAP. Potential confounders/effect modifiers may include, but are not limited to, the following:

- Maternal age
- Previous pregnancy outcomes (e.g. MCMs, stillbirths)
- Pregnancy complications (e.g. preterm labor, preeclampsia and hypertension in pregnancy, eclampsia, placental abruption)
- Comorbidities (e.g. diabetes, hypertension, depression)
- Concomitant exposures (e.g. medications (including fertility treatments and migraine treatments), alcohol, tobacco)
- Paternal demographics (e.g. age)

#### ***Subgroup Analyses and Stratification***

Analyses will be stratified by trimester of exposure and other subgroups of interest, potentially including gestational age at enrollment and maternal age. Additional details on subgroup analyses and stratification will be described in the SAP.

## **9.8. Quality Control**

### **9.8.1. Validation**

Ensuring that the data obtained are of high quality will be an ongoing, multi-step process involving both automatic programming of edit checks for critical data variables in the Cisiv Baseline Plus EDC system as well as visual review for completeness, logic, consistency, and accuracy by the RCC staff. As recommended in regulatory guidance documents, CRFs are carefully designed to ensure data quality and integrity. All patient-reported data will be verified by the appropriate HCP, where possible.

### **9.8.2. Record Retention**

The RCC will retain all study records required by Lilly and by the applicable regulations in a secure and safe facility for the duration of the study. The RCC will consult a Lilly representative before disposal of any study records, and must notify Lilly of any change in the location, disposition, or custody of the study files. Study records with redacted patient identifiers will be transferred to Lilly at the end of the study. Documents that individually and collectively permit evaluation of the conduct of a study and the quality of the data produced will be retained by Lilly for a period of five years in accordance with GPP guidelines. These documents should be retained for a longer period, however, if required by the applicable regulatory requirements.

## **9.9. Limitations of the Research Methods**

Since participation in the study will be voluntary, the included patients may not be representative of the overall US pregnant women population. Because early prenatal testing is so prevalent, it may be difficult to achieve adequate numbers of prospectively enrolled pregnant women if all pregnancies with prior prenatal testing are excluded from the analysis. Therefore, the primary analysis will include pregnancies enrolled prior to outcome but after prenatal test as long as the test does not indicate an abnormality. However, this practice could potentially bias the results by lowering the overall risk of MCMs (Honein et al. 1999). As reporting of pregnancies is totally voluntary, it is possible that even in prospectively reported cases, potential bias could exist. For example, high-risk pregnancies (i.e. one that threatens the health or life of the mother or her fetus) or low-risk pregnancies may be more likely to enroll. Baseline characteristics will be evaluated to identify whether such selection bias may have played a role.

Those pregnancies that have reached EDD, but for which pregnancy outcome information was unobtainable after 4 attempts (1 initial followed by 3 subsequent attempts at 2-week intervals), will be considered lost to follow-up. It is possible that outcomes among pregnancies lost to follow-up could differ from those with documented outcomes. Because of differences in individual reporting patterns, it is currently not possible to assess with any certainty what impact the potential biases the losses to follow-up may have on the analysis. However, efforts at

comparing some of the characteristics of each group may be conducted in an attempt to address this potential source of bias. Following the MACDP convention, calculation of MCM prevalence will exclude fetal losses (SABs, elective terminations, stillbirths, etc.) for which no MCMs have been diagnosed as they may introduce a classification bias. The percentage of these pregnancies consisting of potentially normal outcomes or MCMs is unknown. The data collection form attempts to obtain information on MCMs detected at the time of the outcome. However, the reporting physician may not know the condition of the aborted fetus.

Migraines are associated with some baseline pregnancy risks and comorbidities. It will be important to compare the galcanezumab-exposed, CGRP antagonist-unexposed migraine controls and general population controls for population differences which may potentially result in differential pregnancy outcomes and the introduction of bias.

An important potential limitation of this pregnancy registry is the possibility of lower than expected enrollment. This can result either because galcanezumab is not being prescribed to pregnant women, or because exposed women are not being reported/enrolled into the registry. If enrollment projections are not being met, it will be important to understand why and to identify additional strategies for increasing registry enrollment.

Requiring women to be pregnant at the time of enrollment means that spontaneous abortions occurring early in pregnancy may not be included in the registry. Only recognized spontaneous abortions occurring after enrollment will be captured. It is important to enroll women as early in pregnancy as possible and before the results of prenatal tests are known to maximize the number of prospective enrollments into the registry.

Potential biases related to the composition of the two comparison groups will need to be considered. The non-CGRP antagonist treated migraine controls *may* have been treated with other prescribed or over-the-counter migraine therapies (e.g. anti-epileptic medications including topiramate, tricyclic anti-depressants, beta-blockers, or triptans) which can themselves be associated with pregnancy outcomes, maternal pregnancy complications, and/or maternal comorbidities associated with infant outcomes. If statistically feasible, the impact of type of migraine therapy in this control group could be assessed in sensitivity analyses. Additionally, there may be differences in migraine severity between the galcanezumab-exposed and the CGRP antagonist non-exposed migraine controls. The impact of migraine itself will be taken into account by describing and where possible evaluating the relative occurrence of the study outcomes in the galcanezumab exposed and the non-CGRP antagonist exposed migraine groups vs. the non-migraine control group, as well as potentially with published external comparison data. If the number of women in the registry is small, baseline differences between the exposure cohorts may not be overcome, limiting the ability of the registry to provide meaningful conclusions.

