## PPD

Embryo-fetal development studies conducted in rats and rabbits at exposures up to 29 times the highest proposed clinical dose of 300 mg revealed no evidence of harm to the developing fetus and there were no effects on survival, growth, sexual maturation, behavior, or reproduction in offspring exposed to galcanezumab in utero and through lactation at exposures up to 16 times the highest proposed clinical dose of 300 mg in the prenatal and postnatal development study in rats.

The current nonclinical data and the low number of pregnancy outcomes in humans are insufficient to draw conclusions about the effect or safety of galcanezumab exposure during human pregnancy. However, migraine prevalence is highest in women aged 18 to 49 years (Buse et al. 2012) during typical childbearing years. There is often a medical need for preventive treatment of migraine during pregnancy, with treatment decisions based on clinical judgement of the benefits and the potential harms (Cassina et al. 2010). It is anticipated that given the treated patient population and the long half-life of galcanezumab, exposure during pregnancy will occur in the post-authorization setting and thus, further study is warranted.

Reviews of studies evaluating pregnancy outcome in women with migraine generally conclude that migraine, treated or untreated, probably has no effect on most pregnancy outcomes, including risk of congenital anomalies (MacGregor 2012; Menon and Bushnell 2008). Women with migraine have been reported to be at increased risk of developing hypertensive disorders such as pre-eclampsia in pregnancy compared to women without migraine (Banhidly et al. 2007; Facchinetti et al. 2009) which is associated with an increased risk of low birth weight (preterm birth, small for gestational age infant) (Adeney et al. 2005, Simbar et al. 2010, Facchinetti et al. 2009). In the migraine population, more severe migraine, defined by greater frequency and intensity, is associated with increased prevalence of cardiovascular comorbidity and comorbid affective disorders such as anxiety and depression (Chen et al. 2012; Goulart et al. 2014).

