Another challenge for evaluation of pregnancy, maternal, and fetal/infant outcomes is the known association of some prophylactic migraine medications with congenital malformations and other study outcomes. Therefore, careful selection of comparison populations of women with migraine treated with preventive migraine medication is needed to accurately contextualize event rate .

This prospective, registry-based, observational study to assess maternal and fetal outcomes following exposure to galcanezumab will fulfill a post marketing commitment (PMC) requested by the Food and Drug Administration's (FDA) Center for Drug Evaluation and Research (CDER) and is designed to evaluate pregnancy outcomes as well as maternal and infant events of interest among women exposed to galcanezumab during pregnancy. The design and outcomes are chosen following the FDA request, FDA guidance on pregnancy exposure registries (FDA, 2002), and experience from other pregnancy studies.

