### 9.6.1. Data Processing

Data for this prospective observational safety study will be managed with an electronic data capture (EDC) platform, Cisiv Baseline Plus, which is 21 CFR Part 11 compliant. Only the variables described in the protocol under section 9.3 will be solicited and entered in the EDC. Participants and/or their HCPs will provide data over the phone or by completing a paper case report form (CRF), which can be submitted to the RCC via mail, email or fax. The data will be reviewed by a registry central monitoring associate (CMA) associate for correctness and completeness and entered into the database.

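### The secondary comparison with migraine controls cannot be properly adjusted for migraine severity, because the protocol collects no severity variable

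*Protocol*

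**What the plan says.** The secondary objective (Section 8) is to estimate, where feasible, relative occurrence of the outcomes in exposed women against migraine controls and against women without migraine.

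On severity, Section 9.9 states that "there may be differences in migraine severity between the galcanezumab-exposed and the CGRP antagonist non-exposed migraine controls". Section 7 says why this matters: "In the migraine population, more severe migraine, defined by greater frequency and intensity, is associated with increased prevalence of cardiovascular comorbidity", and the same sentence adds anxiety and depression. Section 7 also reports more hypertensive disorders of pregnancy in women with migraine, and links these to preterm and small infants.

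On data, Section 9.6.1 says: "Only the variables described in the protocol under section 9.3 will be solicited and entered in the EDC". Section 9.3.3 lists maternal age, ethnicity, race, occupation and BMI; three comorbidities (diabetes, hypertension, depression); medications including migraine treatment; and obstetric, prenatal and substance-use items. Nothing there describes how severe or frequent the headaches are, or whether migraine is episodic or chronic. Section 9.4.1.1 records migraine as a concurrent condition, and Table 1 names *disease status* without defining it.

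The potential confounders in Section 9.7.2.1 include comorbidities and migraine treatments. Severity is not named, though the list is open-ended.

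**The concern.** The migraine control group exists to separate the effect of the drug from the effect of the disease. It can do so only if the two migraine groups have similar disease or if the difference can be adjusted for. The protocol expects that they may differ, gives a mechanism by which the difference could affect several outcomes, and then does not collect the variable needed to deal with it.

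Most analysis gaps in a protocol can be closed in the SAP. This one cannot, because adding severity to a model needs a recorded value for each woman. An excess of pre-eclampsia, hypertension, preterm birth or SGA in exposed women could then be attributed to galcanezumab when it reflects more severe migraine. If severity runs the other way, a real excess could be hidden.

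**Working it through.** **1. The plan's own figure.** Section 9.5 gives 420 exposed pregnancies for 80% power to detect a doubling of a 2.78% malformation risk, "relative to women in the general population". No significance level is stated; I assumed 0.05 two-sided, in line with the two-sided 95% intervals of Section 9.7.2. An exact one-sample binomial test against a fixed 2.78% (upper tail 0.025, n = 420) rejects at 20 or more cases, with attained one-sided level 0.015 and power 0.791, close to the stated 80%. As a two-group comparison, 420 against 420 at 2.78% versus 5.56% has 52% power. So the stated size concerns malformations against a background rate. It neither supports nor contradicts the severity point, and nothing below depends on it.

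**2. Is severity collected?** Possible sources, one by one:

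- *Section 9.3.3 and its subsections:* no frequency, intensity, episodic/chronic type or severity.
- *Section 9.4.1.1, concurrent conditions:* presence of migraine only.
- *Table 1, disease status:* undefined and not in Section 9.3. Table 1 and Section 9.6.1 therefore do not agree on what is collected.
- *Medications:* migraine treatment is collected, but Table 1 and Section 9.4.1.1 refer to use during pregnancy. A preventive stopped earlier may not appear, so this is a weak proxy.
- *Hypertension and depression:* collected and listed as confounders. They cover part of the pathway that Section 7 describes, not severity itself.

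**3. Does the non-migraine group solve it?** Section 9.9 proposes comparing each migraine group with the non-migraine group. Write the risks as Re (exposed), Rc (migraine controls) and R0 (no migraine). Then

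(Re/R0) / (Rc/R0) = Re/Rc.

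R0 cancels. Any severity imbalance in Re/Rc is still there after both groups are referred to R0. The step describes the effect of migraine itself, as Section 9.9 says, and not severity within migraine.

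**4. How large could the bias be?** The documents give neither the prevalence of severe migraine nor its risk ratio, so these are assumptions. For a binary severity factor with risk ratio RR, prevalence a in exposed and b in controls, and no true drug effect:

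apparent risk ratio = (1 + a(RR − 1)) / (1 + b(RR − 1)).

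| a vs b | RR 1.25 | RR 1.5 | RR 2.0 |
|---|---|---|---|
| 50% vs 40% | 1.02 | 1.04 | 1.07 |
| 60% vs 30% | 1.07 | 1.13 | 1.23 |
| 70% vs 30% | 1.09 | 1.17 | 1.31 |

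For the last row: 1.35/1.15 = 1.17 and 1.70/1.30 = 1.31. If controls were the more severe group (30% vs 70%), the factors invert to 1.15/1.35 = 0.85 and 1.30/1.70 = 0.76. All values are before adjustment for hypertension, depression or treatment.

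**The case against.** The best defence is that the protocol is not without tools:

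- The contrast is secondary and conditional on feasibility.
- Part of the comorbidity pathway can be adjusted for.
- The confounder list is explicitly non-exhaustive.
- The reporting provider is asked to enrol a migraine control alongside the exposed woman (Section 9.2.4.1), which gives some balance.
- *Disease status* might turn out to hold severity on forms not shown. Since Table 1 carries items that Section 9.3 lacks, the limit in Section 9.6.1 is not applied consistently.
- The bias figures are assumptions and may be small.

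Much of this stands as mitigation. It does not answer the point. An open list does not supply unrecorded data, a control from the same provider is not matched on severity and may be replaced by a self-referred woman, and an undefined item cannot be relied on.

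A reader might go further and infer that women on preventives with "the known association of some prophylactic migraine medications with congenital malformations and other study outcomes" irreparably contaminate the control group, or that the study's primary analysis is compromised. The documents support neither. Section 9.9 does say only that "the impact of type of migraine therapy in this control group could be assessed in sensitivity analyses", but Table 1 collects medications with start and stop dates, and Section 9.7.2.1 lists migraine treatments among the potential confounders to be evaluated. Section 9.2.4.1 also gives a reason for keeping treated controls: untreated women may have milder disease. Excluding women on some preventives could widen the severity gap. And the primary objective is descriptive; this comparison is not part of it.

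**Conclusion.** The point holds for the secondary comparison of exposed women with migraine controls: severity is named as a possible imbalance, linked to relevant comorbidity, and not measured in any defined way.

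Under the assumptions shown, a null effect would read as 1.02 to 1.31 across the grid, and as 1.17 to 1.31 for severe-migraine risk ratios of 1.5 to 2.0 with prevalences of 70% and 30%. The direction assumes that exposed women are the more severe group; the protocol says only that the groups may differ. Adjustment for hypertension and depression could remove part of the bias.

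The outcomes most plausibly affected are hypertensive disorders, preterm birth and SGA. A reader might extend the concern to malformations, but Section 7 reports that migraine probably does not affect their risk, so the documents do not support it for the main outcome.

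**What to change.** 1. Add to Section 9.3.3 and the Registration Form, for both migraine groups: headache diagnosis (episodic migraine, chronic migraine, cluster headache), headache days per month before LMP, and number of prior preventives.
2. Define *disease status* in Table 1 or remove it, and bring Table 1 and Section 9.3 into agreement.
3. Name severity in the Section 9.7.2.1 confounder list and adjust the migraine comparison for it; the SAP can fix the method.
4. Restrict that comparison to exposed women whose recorded indication is migraine. Indication is already requested in Table 1 and Section 9.4.1.1, so this needs no new data.

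The cost is three form items and some missing values. Missingness may be higher in self-referred or obstetric-referred controls, because Section 9.4 limits collection to routinely recorded data, so it should be reported by group. Women enrolled before the change would lack the items unless queried afterwards, so the change is best made before enrolment or early in it.
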